#### 3.1.2 CT scan (or MRI)

For optimal evaluation of patients, the same methods of assessment and technique should be used to characterize each identified and reported lesion at Screening and during follow-up. Contrast-enhanced CT of chest, abdomen and pelvis should preferably be performed using a 5mm slice thickness with a contiguous reconstruction algorithm. CT/MRI scan slice thickness should not exceed 8 mm cuts using a contiguous reconstruction algorithm. If at Screening a patient is known to be allergic to CT contrast or develops allergy during the trial, the following change in imaging modality will be accepted for follow up: a non-contrast CT of chest (MRI not recommended due to respiratory artifacts) plus contrast-enhanced MRI of abdomen and pelvis.

A change in methodology can be defined as either a change in contrast use (e.g. keeping the same technique, like CT, but switching from with to without contrast use or vice-versa, regardless of the justification for the change) or a change in technique (e.g. from CT to MRI,

or vice-versa), or a change in any other imaging modality. A change in methodology will result by default in an “Unknown” overall radiological response assessment. However, another overall radiological response than the Novartis calculated “Unknown” response may be accepted from the investigator if a definitive overall radiological response can be justified to be based on the available information.

In order to calculate the sum of the product of the diameters (SPD) of all index lesions (or extranodal lesions), their size must be entered throughout the study.

Actual lesion measurements should be entered on the corresponding eCRFs. If, during the course of the study, either of the perpendicular diameters of a lesion cannot be reliably measured because of its small size, it is recommended to enter the minimum limit of detection as the diameter size (e.g. 5 mm for spiral CT). In other cases when, during the course of the study, the diameter cannot be reliably measured for reasons other than its size (i.e. borders of the lesion are confounded by neighboring anatomical structures), no measurement should be entered and the lesion cannot be evaluated.

If lesions become confluent over time, it is recommended to measure them as one lesion, report the overall diameters to one of the lesions and assign 0 mm x 0 mm to each of the other previously measured lesions. If a lesion splits during the study, each sub-lesion should be measured separately for all subsequent assessments and all sub-lesions contribute to the SPD.

### **3.1.3 Bone marrow assessment**

Documentation of status of bone marrow involvement by lymphoma based on prior bone marrow biopsy or aspirate findings is required at Screening for all patients.

If no such documentation is available then a bone marrow biopsy or aspirate should be performed at Screening.

If bone marrow involvement is assessed by biopsy, the biopsy sample should have a goal of > 20 mm unilateral core. If the biopsy sample is indeterminate by morphology (immunohistochemistry), then flow cytometry may be performed on bone marrow aspirate to confirm the findings.

### **3.1.4 Physical examination and assessment of B-symptoms**

Skin lesions, if the size is  $\geq 20$  mm in at least one diameter, must be histologically confirmed for lymphoma involvement (the investigational site must document the histological confirmation (yes or no) on the corresponding eCRF) and photographed including a ruler (color photography using digital camera). Tumor assessment will be performed and results will be recorded on the corresponding eCRF at Screening and at Day 1 of every cycle ( $\pm 4$  days) after first dose of study drug..

B-symptoms are of importance in determining prognosis and should resolve completely in patients who have achieved complete response. B-symptoms in lymphoma patients are disease related clinical symptoms and are not caused by anticancer therapy (or drug toxicity).

B-symptoms are defined as follows:

- Significant unexplained fever ( $\geq 38^{\circ}\text{C}$ ),
- Unexplained, recurrent drenching night sweats
- Unexplained loss of  $> 10\%$  body weight within the previous 6 months, as assessed and reported (present vs. absent) by the Investigator.

## 4 Evaluation of Radiological Response

For the sake of simplicity, complete remission and complete response will both be referred to as complete response.

Definitions of Response for Lymphoma patients are listed in Table 5-1. To evaluate disease response to treatment, all index and non-index lesions will be followed and assessed throughout the study. At each assessment, response is evaluated separately for the **index lesions** (Table 4-1) and **non-index lesions** (Table 4-2) identified at Screening, then a combined overall radiological response is determined (Table 4-3).

**Table 4-1 Response Definition for Lymphoma**

Response	Definition	Nodal Masses	Spleen. Liver	Bone Marrow
CR	Disappearance of all evidence of disease	a FDG-avid or PET positive prior to therapy; mass of any size permitted if PET negative  b Variably FDG-avid or PET negative; regression to normal size on CT	Not palpable, nodules disappeared	Infiltrate cleared on repeat biopsy; if indeterminate by morphology, immunohistochemistry should be negative
PR	Regression of measurable disease and no new sites	$\geq 50\%$ decrease in SPD of up to 6 largest dominant masses; no increase in size of other nodes  a FDG-avid or PET positive prior to therapy; one or more PET positive at previously involved site  b Variably FDG-avid or PET negative; regression on CT	$\geq 50\%$ decrease in SPD of nodules (for single nodule in greatest transverse diameter); no increase in size of liver or spleen	Irrelevant if positive prior to therapy; cell type should be specified
SD	Failure to attain CR/PR or PD	a FDG-avid or PET positive prior to therapy; PET positive at prior sites of disease and no new sites on CT or PET  b Variably FDG-avid or PET negative; no change in size of previous lesions on CT		
Relapsed disease or PD	Any new lesion or increase by $\geq 50\%$ of previously involved sites from nadir	Appearance of a new lesion(s) $> 1.5$ cm in any axis, $\geq 50\%$ increase in SPD of more than one node, or $\geq 50\%$ increase in longest diameter of a previously	$> 50\%$ increase from nadir in the SPD of any previous lesions	New or recurrent involvement

Response	Definition	Nodal Masses	Spleen, Liver	Bone Marrow
		identified node > 1 cm in short axis		
		Lesions PET positive if FDG-avid lymphoma or PET positive prior to therapy		

## 4.1 Evaluation of Index Lesions (nodal and extranodal)

### 4.1.1 When index nodal lesions are not in complete response

The response for index lesions is evaluated by calculating the Sum of the Products of Diameters (SPD) of all index lesions (see Table 4-2), except when there is a Complete Response for index nodal lesions (i.e. complete normalization of all index nodal lesions) (see Section 4.1.2).

**Table 4-2 Radiological status based on SPD calculation for all index lesions**

Response Criteria 	Evaluation of index lesions
Complete Response (CR)	See Table 4-4 below (not based on SPD calculation for all index lesions)
Partial Response (PR)	At least 50% decrease from Screening in the SPD of all index lesions
Stable Disease (SD)	Failure to attain the criteria needed for CR or PR and failure to fulfill the criteria for PD
Progressive Disease (PD)	At least a 50% increase from nadir  in the SPD of all index lesions

 At each assessment (if the index nodal lesions are not in CR status), the response status based on SPD calculation will be first assessed for meeting PD status criteria, then PR status and SD status.

 Nadir is defined as the smallest sum of the product of the diameters of all index lesions recorded so far, at or after Screening.

### 4.1.2 When index nodal lesions are in complete response

When there is a Complete Response for index nodal lesions (i.e. complete normalization of all index nodal lesions as defined in Section 4.1.5: all index lesion  $\leq$  15 mm in long axis), the SPD for these index nodal lesions may not be equal to zero and therefore a calculation of a SPD for all index lesions may be misleading. Therefore, by default, a specific response for extranodal index lesions needs to be evaluated, based on the SPD calculation restricted to all index extranodal lesions only (see [Table 4-3](#)).

**Table 4-3 Radiological response criteria for index extranodal lesions in case of CR in index nodal lesions**

Response Criteria 	Evaluation of index extranodal lesions
Complete Response (CR)	Complete disappearance of all index extranodal lesions
Partial Response (PR)	At least 50% decrease from Screening in the SPD restricted to all index extranodal lesions
Stable Disease (SD)	Failure to attain the criteria needed for CR or PR and failure to fulfill the criteria for PD
Progressive Disease (PD)	At least a 50% increase from nadir  in the SPD restricted to all index extranodal lesions

Response Criteria 	Evaluation of index extranodal lesions
 At each assessment, response will be first assessed for meeting CR status. If CR status is not met, response will be assessed for PD status, then PR status and SD status.	
 Nadir is defined as the smallest sum of the product of the diameters restricted to all index extranodal lesions recorded so far, at or after Screening.	

The algorithm for evaluating the response integrating index extranodal lesions and the SPD calculated on all index lesions (where appropriate) provides an overall response for index lesions.

#### 4.1.3 Evaluation of response for all index lesions

The evaluation of response for all index lesions is based on the combination of the response for index nodal lesions (CR or non-CR), the response for index extranodal and the status based on the SPD calculated on all index lesions (nodal and extranodal), as described in Table 4-4.

**Table 4-4 Radiological response for index lesions**

Response for index nodal lesions 	Response for index extranodal lesions 	Status based on SPD calculation for all index lesions	Response for index lesions
CR	CR	Not calculated	CR
CR	SD/ PR	Not calculated	PR
CR	PD	PD	PD
CR	PD	PR	PR
CR	PD	SD	SD
Non-CR	Not evaluated	PD	PD
Non-CR	Not evaluated	PR	PR
Non-CR	Not evaluated	SD	SD

 If no index nodal lesions are present at Screening, then index lesions response is equal to the index extranodal lesions response. A similar rule applied if no index extranodal lesions are present at Screening, then index lesions response is equal to the index nodal lesions response.

In case of missing measurements of any of the index lesions, the radiological response for index lesions at that assessment will be “Unknown (UNK)”, unless progression was seen.

All lesions must have been measured with the same method as the one used at Screening, otherwise the radiological response for index lesions at that assessment will be “Unknown (UNK)”.

#### 4.1.4 Evaluation of non-index lesions (including nodal, splenic and/or hepatic nodules and other extranodal lesions)

At each reassessment, a non-index lesion (or a group of non-index lesions) will be given one of the following designations:

- Normalization (non-index nodal lesion has regressed to normal size; non-index extranodal lesion is no longer present). Normalization of non-index nodal lesions should be determined based on their size at Screening.

- Improved, stable or worsened, but without unequivocal evidence of disease progression (non-index lesion is present but there is not sufficient worsening to declare PD based on the existing non-index lesions).
- Unequivocal evidence of disease progression (worsening of existing non-index lesions is sufficient to declare PD)
- Not assessed

Then, this status for each non-index lesion (or group of non-index lesions) will lead to a global response for non-index lesions (Table 4-5):

**Table 4-5 Response criteria for non-index lesions (nodal, splenic and/or hepatic nodules and other extranodal lesions)**

Response Criteria	Evaluation of non-index lesions
Complete Response (CR)	Complete normalization of all non-index nodal and extranodal lesions: Radiological regression to normal size of all lymph nodes and complete disappearance of all extranodal (including splenic and/or hepatic nodules) lesions
Stable Disease (SD)	Failure to attain the criteria needed for CR and failure to fulfill the criteria for PD
Progressive Disease (PD)	Unequivocal disease progression of any existing non-index lesions (nodal or extranodal)

In case of a missing status of any of the non-index lesions, the radiological response for non-index lesions at that assessment will be “Unknown (UNK)”, unless progression was seen.

All lesions must have been measured with the same method as the one used at Screening, otherwise the radiological response for non-index lesions at that assessment will be “Unknown (UNK)”.

#### 4.1.5 New lesions

The appearance of

- any new nodal lesion >15 mm in any axis. New nodal lesion is defined by:
  - either a previously normal lymph node becoming > 15 mm in any axis,
  - or a previously identified abnormal lymph node showing an increase of at least 50% in the long axis,
  - as assessed by investigator

OR

- any discrete extranodal (including splenic and/or hepatic nodules) lesions reliably appearing on CT scan or MRI after Screening

is always considered as Progressive Disease (PD) and has to be recorded as a new lesion in the appropriate module of the eCRF. Determination of new lymphoma involvement in organs other than lymph nodes or liver or spleen should be confirmed histologically and the site must document that in a comment to the corresponding eCRF.

#### 4.1.6 Overall radiological response

Overall radiological response is calculated as shown in [Table 4-6](#).

**Table 4-6 Overall radiological response at each assessment**

Index lesions	Non-index lesions 	New lesions	Overall radiological response
CR	CR	No	CR
CR	SD	No	PR
PR	CR or SD	No	PR
SD	CR or SD	No	SD
PD	Any	Yes or No	PD
Any	PD	Yes or No	PD
Any	Any	Yes	PD

If no non-index lesions are present at Screening, then this column is not used in evaluating overall radiological response.

If the evaluation of any of the index or non-index lesions identified at Screening could not be made during follow-up or if the index or non-index response is “Unknown (UNK)”, the overall response status at that assessment must be “Unknown (UNK)” unless progression or a new lesion was seen.

#### **4.1.7 Evaluation of overall disease response**

The evaluation of overall disease response at each assessment is a composite of the individual radiological responses (index and non-index lesions, new lesions), laboratory test (bone marrow) and clinical responses (lymphoma related clinical symptoms).

#### **4.1.8 Bone marrow re-assessment at time of radiological CR**

In order to confirm a Complete disease response (CR), bone marrow biopsy or aspirate may be required when a radiological CR has been achieved. Details are provided in the Study Protocol. The infiltrate of lymphoma in bone marrow must have cleared on repeat bone marrow biopsy or aspirate. Patients who achieve a CR by other criteria but who have persistent morphologic positive or inconclusive bone marrow involvement will be considered partial responders. New or recurrent bone marrow involvement anytime during the follow up will be considered PD. Bone marrow biopsy or aspirate will be performed after the first assessment of CR or when clinically indicated.

The biopsy sample of bone marrow must be adequate (with a goal of > 20 mm unilateral core). If the sample is indeterminate by morphology, it should be negative by immunohistochemistry.

#### **4.1.9 Overall disease response**

If a patient has an overall radiological response of CR then this response must be confirmed by bone marrow biopsy or aspirate, presence of normal liver and spleen size, and evaluation of lymphoma related B-symptoms. The patient’s overall response will be calculated as follows:

A patient will be deemed to have overall disease response of CR if bone marrow biopsy or aspirate becomes negative for tumor involvement (if the bone marrow was involved by lymphoma at Screening) and the liver and spleen are normal in size and there are no lymphoma related B-symptoms in addition to radiological CR.

If assessments of any of the following: lymphomatous infiltration of bone marrow, or evaluation of B-symptoms is not done, unknown or indeterminate or B-symptoms are still present when the overall radiological response is assessed as CR or the liver or spleen are enlarged, then the overall disease response will be assessed as PR until evaluation of these factors have shown normalized results and recorded on the corresponding eCRF.

For patients whose radiological response is anything other than CR, assessment of bone marrow, liver, spleen and B-symptoms will not be required in evaluating overall response and overall disease response is the same as radiological response. However any new or recurrent bone marrow involvement at any time during follow-up will be considered PD.

Of note, appearance of B-symptoms or enlarged spleen or liver will not in themselves constitute documentation of progression. They are however expected to be associated with progressive disease. Every effort should be made to document that evidence radiologically and report the corresponding tumor assessments. Such tumor assessments are expected to be performed within 2 months of appearance of B-symptoms or enlarged spleen or liver.

## Appendix D: Ann Arbor staging classification

---

**Stage Area of involvement**

---

- I Single lymph node group
- II Multiple lymph node groups on the same side of the diaphragm
- III Multiple lymph node groups on both sides of the diaphragm
- IV Multiple extranodal sites or lymph nodes and extranodal disease
- X Bulk disease > 10 cm
- E Extranodal extension or single isolated site of extranodal disease

Class A are patients who experience no B symptoms

Class B are patients experience unexplained fever of  $\geq 38^{\circ}\text{C}$ ; unexplained, recurrent drenching night sweats; or unexplained loss of >10% body weight within the previous 6 months

---

Cotswolds modification of Ann Arbor staging system adapted from 2007 NCCI guidelines for non-Hodgkin's lymphoma

---

## Appendix E: Rai Staging Systema

Stage	Area of involvement	Risk Status
0	Lymphocytosis, lymphocytes in blood $>15 \times 10^9/L$ and $>40\%$ lymphocytes in bone marrow	Low
I	Stage 0 with enlarged node(s)	
II	Stage 0-1 with splenomegaly, hepatomegaly, or both	Intermediate
III b	Stage 0-II with hemoglobin $<11.0 \text{ g/dL}$ or hematocrit $<33\%$	Intermediate
IV b	Stage 0-III with platelets $<100 \times 10^9/L$	High
		High

a Research originally published in Blood. Rai KR,et al. Clinical staging of chronic lymphocytic leukemia. Blood 1975;46(2):219-234. (c) The American Society of Hematology

b Immune-mediated cytopenias are not the basis for these stage definitions.

[figure not shown]
[figure not shown]
## Appendix F: Criteria for Response assessment in Acute Myeloid Leukemia (based on IWG and Cheson)

Disease assessments will be based on standardized response criteria as defined by the International Working Group (IWG) for AML ([Cheson, et al 2003](#)).

Response classification in AML at a given evaluation time (Cheson 2003)	
Response category	Definition #
Complete remission (CR)	
Bone marrow            < 5% blasts            no blasts with Auer rods
 
Peripheral blood            neutrophils <math>\geq 1.0 \times 10^9/L</math>            platelets <math>\geq 100 \times 10^9/L</math>  <math>\leq 1\%</math> blasts            No evidence of extramedullary disease (such as CNS or soft tissue involvement). Transfusion independent (see Section 7.2.1.4.5).
 
In case all criteria for CR apply and the patient receives platelet and/or neutrophil transfusions, the patient will be assessed as CRI.

Complete remission with incomplete blood count recovery (CRI)	
Bone marrow            < 5% blasts            no blasts with Auer rods
 
Peripheral blood            neutrophils <math>< 1.0 \times 10^9/L</math> and/or platelets <math>< 100 \times 10^9/L</math>  <math>\leq 1\%</math> blasts            No evidence of extramedullary disease (such as CNS or soft tissue involvement). Transfusion-independent (see Section 7.2.1.4.5). Exception: Platelet and neutrophil transfusions are allowed.

Partial Remission (PR)	
Bone marrow            50% or greater decrease (absolute range 5-25% blasts)            < 5% of blasts contain Auer rods
 
Peripheral blood            neutrophils <math>< 1.0 \times 10^9/L</math> and/or platelets <math>< 100 \times 10^9/L</math>            No evidence of extramedullary disease (such as CNS or soft tissue involvement).

Treatment failure	Treatment failure includes those patients for whom treatment has failed to achieve PR, CRI or CR throughout the treatment.
Relapse from CR or CRI *	Only in patients with a CR or CRI: Reappearance of blasts in peripheral blood ( $> 1\%$ ) OR $\geq 5\%$ blasts in bone marrow OR (Re-)appearance of extramedullary disease
No response	In case a patient does not achieve CR, CRI, PR or relapse for an individual response assessment.
Unknown	In case the response assessment was not done, the baseline assessment was not done, the assessment was incomplete or was not done within the respective time frame.

# If not defined otherwise, all of the criteria apply.

\*[Cheson et al \(2003\)](#) does not specify relapse after PR.

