### Response Definition for Chronic Lymphocytic Leukemia

#### Group A Response for Tumor Burden

Response	Nodal Masses	Organomegaly	Bone Marrow
CR	None > 1.5 cm	No splenomegaly No hepatomegaly	Normocellular >30% Lymph. No B lymphoid nodules
CRi	None > 1.5 cm	No splenomegaly No hepatomegaly	Hypocellular marrow
PR	Decrease ≥50%	Spleen/Liver decrease ≥50	50% reduction in marrow infiltrate, or B-lymphoid nodules

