#### Group B Response for hematopoietic system^2

Response	Platelet count	Hemoglobin	Neutrophils
CR	>100 x 10  /L	>11 g/dL	>1.5 x 10  /L
CRi	If meets criteria from Group A but does not meet criteria from Group B		
PR	>100 x 10  /L or increase ≥50% over baseline	>11 g/dL or increase ≥50% over baseline	>1.5 x 10  /L or >50% improvement over baseline
SD	Failure to attain CR/CRi/PR or PD		
Relapsed disease or PD	Appearance of any new lesions; at least one of the above criteria. Isolated progressive lymphocytosis in the setting of reduced lymph node size or organomegaly or improvement in hemoglobin/platelets will not be considered progressive disease		

 Hallek M, et al. Guidelines for the diagnosis and treatment of chronic lymphocytic leukemia updating the National Cancer Institute-Working Group 1996 Guidelines. Blood 2008; 111:5446-5456

 All values are without transfusion or hematopoietic growth factors

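### As printed, AML partial remission excludes patients whose blood counts have recovered, and the CLL progression row has no usable rule for worsening of existing disease

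*Protocol*

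**What the plan says.** For hematologic tumors, Protocol Section 10.4 sends the primary endpoint, clinical benefit rate (CBR), to the disease-specific appendices. Section 10.5.1 does the same for overall response rate (ORR). SAP Section 4.1 counts CR, PR, or SD for at least 16 weeks as clinical benefit.

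**AML (Appendix F).** The PR row requires:
- in marrow, "50% or greater decrease (absolute range 5-25% blasts", with fewer than 5% of blasts containing Auer rods;
- in blood, neutrophils below 1.0 and/or platelets below 100 x 10^9/L, the same count line as in the row for complete remission with incomplete count recovery (CRi);
- no extramedullary disease.

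The footnote reads "If not defined otherwise, all of the criteria apply". The residual category, *No response*, is defined as "In case a patient does not achieve CR, CRI, PR or relapse for an individual response assessment". There is no SD row.

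**CLL (Appendix J).** Group A (tumor burden) has rows for CR, CRi and PR only. Group B (hematopoietic function) adds SD, defined as whatever is neither a response nor PD. Its PD row reads "Appearance of any new lesions; at least one of the above criteria". The rest of that row is an exclusion: "Isolated progressive lymphocytosis in the setting of reduced lymph node size or organomegaly", or with improving hemoglobin or platelets, is not progression. Protocol Section 7.2.1.4 assesses CLL by Appendix J and takes only the assessment schedule from lymphoma.

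**The concern.** A response table should not score a patient lower because an additional measure is better. The AML PR row does so: recovered counts disqualify a marrow response that low counts would allow. In the same table, the CR and CRi rows order counts the other way, with recovered counts giving the better category.

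A progression row should say what worsening is. The CLL row does so only for new lesions. Its second clause refers upward, and the rows above it are response thresholds and the residual SD row. Appendices B, C, H and L (RECIST, lymphoma, ALL and myeloma) each state a quantitative increase that counts as progression, so the gap in Appendix J looks like an omission.

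The two errors act in opposite directions. The AML wording can remove a success from CBR and ORR. The CLL wording can turn progression into SD lasting 16 weeks or more, which is a CBR success, and can delay a PFS event.

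**Working it through.** The plan gives no figure to reproduce here. The check applies the printed rules to test patients.

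**AML.** Inputs from Appendix F: a blast fall of at least 50% ending in 5-25%, the low-count line, and all criteria joined by AND. Take blasts falling from 40% to 12%, no extramedullary disease, and the Auer-rod criterion met.

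- Blast fall: (40 - 12)/40 = 70%, and 12% lies in 5-25%, so the marrow criterion is met.
- CR and CRi both need marrow blasts below 5%, so neither applies.
- PR then turns on the counts (x 10^9/L):

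| Neutrophils | Platelets | As printed | Count line removed | Recovery of both counts required |
|---|---|---|---|---|
| 0.6 | 60 | PR | PR | No response |
| 0.6 | 140 | PR | PR | No response |
| 1.4 | 60 | PR | PR | No response |
| 1.4 | 140 | No response | PR | PR |

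As printed, the patient with the best counts receives the worst category. The last two columns show that the two possible corrections are not equivalent.

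**CLL.** Take a patient whose existing nodes have doubled. Group A has no CR, CRi or PR, so the category is PD or SD. The clause about the criteria above can be read three ways. Good counts are platelets 140, hemoglobin 12 and neutrophils 2.0; poor counts are 60, 9 and 1.0.

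| Reading of the PD row | No new lesion, good counts | No new lesion, poor counts | New lesion, good counts | New lesion, poor counts |
|---|---|---|---|---|
| New lesion is the only working criterion | SD | SD | PD | PD |
| New lesion OR any threshold above | PD | SD | PD | PD |
| New lesion AND any threshold above | SD | SD | PD | SD |

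No reading responds to the doubled nodes. Under OR, good counts are what make the patient PD, and a patient meeting the CR count thresholds would also satisfy PD. Under AND, a new lesion with poor counts is only SD. With poor counts and no new lesion, all three readings give SD.

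**The case against.** The strongest defense is that other parts of the plan do some of the work. Response is assessed by the investigator, and Appendices F and J and Section 7.2.1.4 name the published criteria behind the tables. SAP Section 4.1 treats disease as progressive when progression is given as the reason for stopping treatment or the cause of an on-treatment death. SAP Section 4.4 makes progression as the discontinuation reason a PFS event. A CLL patient taken off drug for growing nodes before 16 weeks is therefore not a clinical benefit, whatever Appendix J says. This stands and limits the CLL harm to patients whose growth is not called progression. It does nothing for AML, where the printed rule withholds a response.

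A reader might also infer more than the documents support:

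- *That any improved AML patient is scored No response.* Three of the four test patients are PR; only recovery of both counts causes the loss.
- *That CLL has no worsening criterion, or that growing nodes are always SD.* New lesions are named, and the literal OR reading can give PD. The text is indeterminate.
- *That the CLL complete-response marrow entry, "Normocellular >30% Lymph. No B lymphoid nodules", has its sign reversed because Appendix E lists more than 40% "lymphocytes in bone marrow" under Rai stage 0.* A staging element sets no response threshold, the source criteria are not available here, and a symbol may have been misread from the PDF.
- *That one patient moves a three-patient cohort's CBR by 33 points.* SAP Section 4.1 only lists hematologic types with fewer than 4 patients. Entry to the Bayesian model also needs a control rate, and none is given for AML or CLL. The primary decision is a posterior with borrowing, not a raw rate.
- *That Appendix C supplies the missing liver and spleen rule.* Its rule concerns the measured size of previous lesions, and its Section 4.1.9 says organ enlargement alone does not document progression.

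**Conclusion.** Both defects hold on the internal logic of the appendices.

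In AML, a patient with a blast fall of at least 50% to 5-25%, neutrophils of at least 1.0 and platelets of at least 100 x 10^9/L is *No response*, while the same marrow with either count low is PR. With no SD category, that assessment counts for neither CBR nor ORR. The result applies assessment by assessment: a patient scored PR earlier, while a count was low, might keep that as best response.

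In CLL, worsening of existing nodes, liver or spleen and falling counts have no usable PD rule and can default to SD. The SAP rules on discontinuation and on-treatment death contain this only in part.

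The size cannot be stated, because the documents give no AML or CLL numbers. For illustration, assume a hematologic type large enough to be summarized under SAP Section 4.1. One misclassified patient then moves its raw CBR by 1/4 = 25 points at n = 4 and 1/10 = 10 points at n = 10. That is not the effect on the Bayesian decision. The finding does not depend on any comparison with the cited source criteria.

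**What to change.** **Appendix F.** Remove the low-count requirement from the PR row so that recovered counts cannot disqualify a PR. If the sponsor meant count recovery to be required, the row should say so instead; as the AML table shows, that choice scores low-count patients differently. Re-derive AML CBR and ORR from the counts and marrow results already collected.

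**Appendix J.** The sponsor should reconcile the PD row with the response criteria it cites, so that the row refers to worsening of existing disease and of counts as well as to new lesions. Progression ends study treatment, so this review does not propose a threshold. Recheck CLL assessments already scored, for CBR and for PFS dates.

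**Cost.** Wording changes in two appendices and a re-derivation for the AML and CLL patients, if any. Blood counts, marrow results and imaging are database items in Table 7-1, so no new data are needed. The clinical study report should give the number of AML and CLL patients and say whether any category changed.
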